	
B. Locally advanced unresectable disease (see the criteria for resectability from inclusion criteria) or evidence of metastatic disease.
 
C. Any other invasive malignancy within the past three years.
 
D. Presence of any known contraindications to or hypersensitivities to the investigational products.
 
E. Use of strong CYP3A4 inhibitors or inducers, which cannot be discontinued prior to study entry.
 
F. A non-surgical candidate.
 
G. Subject is unable to understand, provide consent or comply with study requirements, treatments or instructions in the opinion of the treating physician.
 
H. Uncontrolled diarrhea, active infection, known interstitial lung disease or other medical condition that precludes safe administration of this combination therapy consistent with manufacturer recommendations.
 
I. Unwilling/unable to comply with birth control requirements while on study.
 
J. Females or males of childbearing potential who are unwilling or unable to use an acceptable method to avoid pregnancy for the entire study period and for at least 7 months for females and 4 months for males after the last dose of study drug.
 
K. Females who are pregnant or breastfeeding.
 
L. History of any other disease, metabolic dysfunction, physical examination finding, or clinical laboratory finding giving reasonable suspicion of a disease or condition that contraindicates the use of protocol therapy or that might affect the interpretation of the results of the study or that puts the subject at high risk for treatment complications, in the opinion of the treating physician.
 
M. Prisoners or subjects who are involuntarily incarcerated.
 
N. Subjects who are compulsorily detained for treatment of either a psychiatric or physical illness.
 
O. Subjects demonstrating an inability to comply with the study and/or follow-up procedures.
 
P. Known dihydropyrimidine (DPD) deficiency

Efficacy Assessments:	4 to 8 weeks after completion of neoadjuvant chemotherapy subjects will undergo surgical resection. The primary endpoint is the complication rate for evaluable patients who complete surgery, and

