### 6.3 Pre-surgical Evaluation (within 4 weeks prior to surgery)

Pre-surgical evaluations should be within four to eight weeks following the last dose of chemotherapy.

- a. Height, weight and ECOG performance status will be obtained from each subject.
- b. An interim medical history and physical exam, including vital signs, will be obtained from each subject.
- c. Blood samples for a CBC with differential count, comprehensive metabolic panel, and CA 19-9 will be obtained.
- d. Research blood samples
- e. CT of chest/abdomen and pelvis with IV contrast (or MRI of abdomen/pelvis with non-contrast chest CT, if IV contrast is contraindicated) should be performed following, but no more than 4 weeks after the administration of the last cycle of neoadjuvant chemotherapy.
- f. Response Evaluation Criteria in Solid Tumors (RECIST) Version 1.1 will be utilized to assess tumor response
- g. ECG (as medically indicated)
- h. FACT-G, quality of life assessment.
- i. Microbiota sample collection (after completion of chemotherapy **and** after completion of radiotherapy if performed). Stool collection may be performed at home and mailed or brought to clinic, or obtained in clinic. Urine and oral samples will be collected in clinic.

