#### Overall treatment plan

- ONIVYDE® with 5-fluorouracil, leucovorin and oxaliplatin (NALIRIFOX) at the recommended for phase II doses determined from NCT02551991-IV dosing every 2 weeks x 8 total treatments (4 months)
- Surgical resection in the absence of documented progression within 4-8 weeks following last dose of therapy. Clinical response assessment following last cycle of NALIRIFOX.
- Optional chemoradiotherapy with evidence of local disease progression or as otherwise defined in Section 7.2.4
- Optimal supportive care and growth factor support per recommendations from NCT02551991
- Clinical follow-up 4-6 weeks post-operatively (EOT visit)
- Survival follow-up every 6 months for 5 years and documentation of any recurrence.

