#### 7.2.4 Radiotherapy

External beam radiotherapy is only allowable following completion of neoadjuvant chemotherapy and study drug treatment based upon repeat imaging and clinical assessments at the pre-operative time point with either of the following scenarios:

- 1) Evidence of local disease progression that is resulting in uncontrolled pain, obstruction or other clinically relevant complication suggestive of conversion to a locally advanced clinical stage.
- 2) Radiographic evidence at the time of surgical planning of local disease persistence that, in the opinion of the treating surgeon and with consensus of the multidisciplinary tumor board, jeopardizes the ability to attain a margin negative surgical outcome.

The schedule of radiotherapy in this protocol should conform to the following parameters:

Radiation planning and dosing:

- Supine with arms up in VacLoc immobilization.

---

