### 11.2 Period of Observation

Following the subject's written consent to participate in the study, all SAEs must be collected, including those thought to be associated with protocol-specified procedures. Collection of all SAEs must continue until the post-op visit (or pre-op visit if the subject does not proceed with surgery). If applicable, SAEs must be collected that relate to any later protocol-specified procedure (e.g., protocol-specified resection surgery). SAEs not related to a later protocol-specified procedure will not be collected beyond 30 days post last dose of study treatment. The investigator should notify the DISC of any SAE occurring after this time period that is believed to be related to the investigational product or protocol-specified procedure.

The investigator will begin collecting non-serious adverse event (NSAE) information once administration of the investigational product is initiated. This NSAE information should also be collected from the start of a placebo lead-in period or other observational period intended to establish a baseline status for the subjects. Treated subjects, including those who were prematurely discontinued from the study, will be followed for any adverse events that occur during the study until the post-op visit (or pre-op visit if the subject does not proceed with surgery). However, after 30 days post last dose of study treatment, only unexpected AEs related to a protocol-specified procedure (e.g. resection surgery and associated hospitalization) will be reported. If another course of anti-cancer therapy is initiated prior to the that follow-up period visit, collection of adverse events will no longer be performed, with the exception of events that may be possibly, probably, or definitely related to the investigational agent or are clinically significant.

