#### 12.5 Analysis of Safety Data

Safety analyses will be performed on all patients who receive any dose of study medication. Adverse events that occur more than 30 days after the administration of the last dose of treatment will not be included. Safety evaluation will be performed based on the actual therapy received. The safety and tolerability of study drug is determined by reported Aes, physical examinations, laboratory tests, and ECGs. All patients will be assessed regularly for potential occurrence of Aes from the time that treatment starts until 30 days after the last dose of study therapy or 30 days post-operatively, whichever is longer. Aes will be summarized with the incidence and percentage of patients with at least one occurrence of a preferred term (according to the most severe NCI-CTCAE Version 4.0 grade) will be included. The number of Aes reported will also be summarized. Causality (relationship to study drug) will be summarized separately. Duration of AE will be determined and included in listings along with action taken and outcome. Laboratory results will be classified according to NCI-CTCAE, Version 4.0. Incidence of laboratory abnormalities will be summarized; laboratory results not corresponding to an NCI-CTCAE Version 4.0 term will not be graded. Laboratory toxicity shifts from baseline to worst grade will also be provided. The results from physical examination and vital sign measurement will be tabulated. Descriptive statistics will be provided as appropriate.

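### Section 12.5 drops adverse events from day 31 after the last dose, yet assesses them to 30 days after surgery, so 28-30 of the 30 post-operative days are left out of the graded AE tables

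*Combined protocol and SAP*

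**What the plan says.** Section 12.5 (Analysis of Safety Data) sets two time limits in one paragraph.

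- Exclusion from analysis: "Adverse events that occur more than 30 days after the administration of the last dose of treatment will not be included".
- Assessment: patients are followed for AEs "until 30 days after the last dose of study therapy or 30 days post-operatively, whichever is longer".

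The 12.5 tables give the worst CTCAE grade per preferred term, the number of events and, separately, relationship to study drug. Listings add duration, action taken and outcome.

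Timing of surgery: the synopsis states that "4 to 8 weeks after completion of neoadjuvant chemotherapy subjects will undergo surgical resection", and the overall treatment plan in section 7.1 has "Surgical resection in the absence of documented progression within 4-8 weeks following last dose of therapy".

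Section 11.2 (Period of Observation) governs what is collected. SAE collection continues to the post-operative visit, but from 30 days after the last dose it is restricted to SAEs related to a later protocol-specified procedure, with resection as the example. For other AEs, "However, after 30 days post last dose of study treatment, only unexpected AEs related to a protocol-specified procedure" are reported. Appendix I gives capturing surgical complications as the purpose of the current rule for this later period.

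Section 12.2 analyses the primary endpoint, a yes/no composite of 30-day post-operative complications, on its own and with an exact confidence interval.

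**The concern.** The primary objective is safety and feasibility before pancreatic resection, and the background describes the main goal as establishing perioperative safety. Section 12.2 will show how many operated subjects had a qualifying complication. It will not show which toxicities occurred, at what grade, or how they were attributed. That is the job of the 12.5 tables, and the exclusion sentence stops them at about the time of surgery.

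The plan therefore collects surgical AEs under 11.2 and then leaves them out of its only graded AE summary, without saying where else they are reported. A post-operative death, for example, would count in the 12.2 composite but, if it fell after day 30, would not appear as a grade 5 event in 12.5. Two analysts following 12.5 in good faith could also produce different tables, one using the exclusion sentence and the other the assessment window.

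**Working it through.** The plan states no figure to reproduce; the check is a day count.

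**Inputs**
- Day 0 = last dose of study drug.
- Cut-off = day 30 (12.5, exclusion sentence).
- Surgery on day S, with S from 4 × 7 = 28 to 8 × 7 = 56 (synopsis; section 7.1).
- Post-operative days = study days S+1 to S+30 (12.5, assessment window; the same 30 days as in 12.2).

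**Post-operative days beyond the cut-off**

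Days inside = max(0, 30 − S); days outside = 30 − days inside.

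| Surgery day S | Inside | Outside | Share outside |
|---|---|---|---|
| 28 | 2 | 28 | 28/30 = 93.3% |
| 29 | 1 | 29 | 29/30 = 96.7% |
| 30 to 56 | 0 | 30 | 30/30 = 100% |

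**Days beyond the cut-off up to and including surgery**

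max(0, S − 30) = 0 (S = 28) to 26 (S = 56).

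**Share of 12.5's own assessment window that the exclusion removes**

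The window ends on day S + 30, so on day 58 to 86. Days removed = (S + 30) − 30 = S.
- S = 28: 28/58 = 48.3%.
- S = 56: 56/86 = 65.1%.

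**Sensitivity to the clock**
- If the 30 days ran from the end of the 46-hour 5-FU infusion while surgery was counted from its start, the cut-off would be about day 32. The range becomes 26-30 of 30 days, with the same conclusion.
- Where pre-operative radiotherapy is given, section 7.2.4 plans surgery 4-8 weeks after its last dose. If the clock ran from that dose, the count is again 28-30. If it ran from study drug, surgery is later still and the count is the same or higher.

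**After the fix**

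With the cut-off moved to the end of 12.5's own window, 0 of 30 post-operative days are excluded.

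**The case against.** The strongest reply is that the exclusion is a deliberate drug-safety window. Section 12.5 speaks of the safety and tolerability of study drug, and its only causality summary is relationship to that drug. Thirty days after the last dose suits that purpose, and the two sentences can then be read as one rule for follow-up and another for analysis. This partly stands: a drug-period table is sensible and should stay visible. But the exclusion works by time, not by cause. It would also remove a late SAE believed to be drug-related, which 11.2 asks investigators to notify to the safety committee. And if the window is deliberate, 12.5 still has to say where the post-operative AEs are summarised.

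It is also true that the loss is smaller than the day counts suggest. Readmission, death, reoperation or intervention, and major complications prolonging the stay are analysed in 12.2. After day 30, 11.2 collects only procedure-related SAEs and unexpected procedure-related AEs, so what is left out is a limited set. Both points stand.

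A reader might go further and infer that 11.2 leaves a large hole around the optional radiotherapy ("Optional chemoradiotherapy with evidence of local disease progression or as otherwise defined in Section 7.2.4"). The documents do not support a size for it.
- It is not stated whether the last dose of study treatment includes chemoradiotherapy.
- The number irradiated and the start day are not given. The decision is "based upon repeat imaging and clinical assessments at the pre-operative time point"; section 6.3 has "Pre-surgical evaluations should be within four to eight weeks following the last dose of chemotherapy", yet the same section and Appendix A want the imaging no more than 4 weeks after the last cycle.
- If radiotherapy counts as another course of anti-cancer therapy, the stop rule in 11.2 still keeps clinically significant events and those at least possibly related to the investigational agent. Any gap is then partial.

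The unclear clock is worth a query to the sponsor, but it is not part of this finding.

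**Conclusion.** The inconsistency is in the current text of 12.5. For every subject operated on schedule, 28-30 of the 30 post-operative days (93-100%) fall after the analysis cut-off, so procedure-related SAEs and unexpected procedure-related AEs collected then would be missing from the graded AE tables. The result assumes surgery on day 28-56 after the last dose. It changes only to 26-30 days if the clock starts at the end of the infusion, and does not shrink if it starts at radiotherapy.

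Two stronger readings should be resisted. The primary endpoint does not lose these complications, because 12.2 counts them independently of 12.5. Nor do the percentages mean that 93-100% of post-operative toxicity is lost: they are proportions of calendar days, and the documents give no event rate by day.

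This is a point for the sponsor to consider. It is a stated rule that discards collected perioperative data in a trial about perioperative safety, and it is cheap to correct.

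**What to change.** In 12.5, replace the exclusion sentence with:

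> The safety tables include AEs up to the later of day 30 after the last dose of study drug and day 30 after surgery. Three periods are tabulated separately: on-treatment (to day 30 after the last dose of study drug, and before surgery); post-operative (from surgery to day 30 after it); and, where there is time between them, the pre-operative interval, including any protocol radiotherapy.

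Footnote the tables:

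> After day 30 following the last dose of study drug, AEs are limited to those collected under section 11.2.

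Naming study drug fixes the clock for these tables. With surgery on day 28 there is no interval, and the post-operative table covers days 28-58. With surgery on day 56 the interval is days 31-55, and the post-operative table covers days 56-86. For subjects who do not have surgery, the tables still end at day 30.

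Cost: one or two extra tables and a slightly higher reported toxicity rate. Ascertainment after day 30 remains limited, which is why the periods are kept apart and footnoted. No new visit, data field or change to 11.2 is needed.

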#### 12.6 Enhanced AE Safety Monitoring

When accrual is greater than 10 subjects, if at any time, 5 of the initial 10 treated subjects or 50% or more of all treated subjects have experienced a non-hematologic grade  $\geq$  3,4, 5 adverse event considered at least possibly related to treatment (possible, probable, or

definite), accrual will be temporarily suspended to this study for a review by the PI and the Data Integrity and Safety Committee. Grade 4 and 5 adverse events deemed “unrelated” or “unlikely to be related” will be reviewed and monitored, to assess for the emergence of a previously unrecognized treatment-related adverse event.

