### 12.1 Sample Size Determination

For this prospective phase II pilot study, the sample size justification is based on the primary endpoint, the complication rate for evaluable patients who complete surgery. A sample size of 25 patients achieves ~80% to detect a reduction of 20% in the 30-day post-operative complication rate (from 30% to 10%), using a one-sided exact test with a significance level of 0.05. Assuming 10% drop-out rate, we will accrue a total of 28 patients for this study. The study expects a 20-month accrual period with an additional follow-up of 7 months after the last patient is enrolled. The sample size calculation is conducted by PASS 16.

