### **13. DATA AND SAFETY MONITORING**

#### **13.1 Data Integrity and Safety Committee**

This protocol will be reviewed and monitored by the University of Florida Health Cancer Center (UFHCC) DISC in accordance with their policies and procedures. They will review and monitor study progress, toxicity, safety and other data from this trial. Questions about subject safety or protocol performance will be addressed with the sponsor-investigator, statistician and study team members. Should any major concerns arise; the DISC will offer recommendations regarding whether or not to suspend the trial.

UFHCC DISC data and safety monitoring activities include:

- Review of clinical trial conducted for progress and safety
- Review of all adverse events requiring expedited reporting as defined in the protocol
- Review of reports generated by data quality control review process
- Notification of the sponsor-investigator of recommended action
- Notification of sites coordinated by the UFHCC of adverse events requiring expedited reporting and subsequent committee recommendations for study modifications

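### The accrual gate in Section 12.6 can delay a mandatory suspension whose fixed-count trigger, 5 of the first 10 treated, has already been irreversibly met

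*Combined protocol and SAP*

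**What the plan says.** Section 12.6 (Enhanced AE Safety Monitoring) sets one opening condition, accrual above 10, and then two alternative triggers. The condition and the first trigger, a fixed count, read "When accrual is greater than 10 subjects, if at any time, 5 of the initial 10 treated subjects". The second is a running proportion, "50% or more of all treated subjects have experienced a non-hematologic grade" 3 to 5 event at least possibly related to treatment. If either is met, "accrual will be temporarily suspended to this study for a review by the PI and the Data Integrity and Safety Committee".

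Section 12.1 gives the pace: "Assuming 10% drop-out rate, we will accrue a total of 28 patients for this study", and "The study expects a 20-month accrual period". Sections 3.1 and 7.1 give eight treatments, one every two weeks.

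Other safety oversight carries no numeric trigger. Under Section 13.1, "Should any major concerns arise; the DISC will offer recommendations regarding whether or not to suspend the trial". Section 11.4.1 sends SAEs to the project office within 24 hours and to the DISC within 5 days. Section 13.3 makes the PI primarily responsible for monitoring adverse events, and Section 15.9 makes them a standing item at weekly site meetings.

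The protocol gives no operating characteristics for the 12.6 rule.

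**The concern.** The two limbs behave differently as data come in. A running proportion can rise and fall, and with very few subjects it is unstable, so a minimum number is sensible there. A count of five within a fixed group of ten cannot fall. Once the fifth qualifying subject is seen, whether that is subject 5, 6, 7, 8 or 9, the count is settled. Later subjects add nothing to the decision whether this limb is met.

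The opening condition nevertheless applies to both limbs. If five of the first seven subjects had qualifying toxicity, the text would not require suspension until an eleventh had been accrued. At stake is the exposure of a few extra subjects, in a trial of 28 whose primary objective is safety and feasibility, after a count the protocol itself treats as grounds for a pause. The wait gives this limb no protection against false alarms in return.

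**Working it through.** **Inputs.** From 12.6: the rule becomes active at the 11th accrual, and the fixed count is 5 of the first 10 treated (taken as at least 5). From 12.1: 28 subjects in 20 months, so 28/20 = 1.4 per month. From 3.1 and 7.1: eight two-week cycles, 8 × 14 = 112 days, about 3.7 months. Assumptions: true qualifying-event rates p of 30% to 70%, independent subjects, accrual and treatment counts in step. There is no stated figure to reproduce.

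**Step 1. Further accruals when events are known at once.** If the fifth event is in subject t, the accruals up to and including subject 11 number 11 − t:

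| t | 5 | 6 | 7 | 8 | 9 | 10 |
|---|---|---|---|---|---|---|
| 11 − t | 6 | 5 | 4 | 3 | 2 | 1 |

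Six accruals take 6/1.4 = 4.3 months, and two take 2/1.4 = 1.4 months.

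**Step 2. Distribution of t.** P(t) = C(t−1, 4) p⁵ (1−p)^(t−5). At p = 0.5, for t = 5 to 10, this gives 0.0312, 0.0781, 0.1172, 0.1367, 0.1367 and 0.1230, which sum to 0.623. The weighted sum of (11 − t) is 1.854, so the mean given a trigger is 1.854/0.623 = 2.98.

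| p | P(5 by subject 10) | P(5 by subject 9) | P(t = 5) | Mean further accruals given a trigger |
|---|---|---|---|---|
| 0.3 | 0.150 | 0.099 | 0.002 | 2.3 |
| 0.4 | 0.367 | 0.267 | 0.010 | 2.6 |
| 0.5 | 0.623 | 0.500 | 0.031 | 3.0 |
| 0.6 | 0.834 | 0.733 | 0.078 | 3.5 |
| 0.7 | 0.953 | 0.901 | 0.168 | 4.1 |

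Given a trigger at p = 0.5, the fifth event has occurred by subject 9 in 0.500/0.623 = 80% of cases.

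**Step 3. Trigger probability with and without the gate.** Five events by subject 10 is the same event whether it is acted on at once or at subject 11. The second column is therefore the trigger probability of this limb under either wording.

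**Step 4. Event timing.** Toxicity can appear at any point over eight cycles, and 1.4 × 3.7 ≈ 5 subjects enter in that time. I simulated even entry at 1.4 per month, with each event uniform over a window after the subject's entry. Further accruals are max(0, 11 − number accrued at the fifth event). Means given a trigger:

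| Event window | p = 0.5 | p = 0.6 | p = 0.7 |
|---|---|---|---|
| Known at once | 3.0 | 3.5 | 4.1 |
| First 4 weeks | 2.8 | 3.3 | 3.9 |
| First 8 weeks | 2.2 | 2.7 | 3.3 |
| About 3.7 months | 1.2 | 1.6 | 2.1 |

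With the 3.7-month window the gate causes no delay in 44%, 32% and 20% of triggering cases at these rates. All six extra subjects arise in under 1% of triggering cases.

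**Step 5. What the gate does for the other limb.** Without a minimum number, the chance that the running proportion reaches 50% at some point within the first 10 subjects is 0.40 at p = 0.2 and 0.59 at p = 0.3, because 1 of 1 or 1 of 2 would be enough. The gate is useful there.

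**The case against.** A reader might infer that the rule forces enrolment to continue, that about six more subjects would typically enter, and that they would be enrolled for no gain in information. The documents do not support any of these.

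- **Enrolment is not compelled.** Section 12.6 adds a mandatory trigger and does not bar earlier suspension. The PI and DISC receive the relevant events under 11.4.1, 13.1, 13.3 and 15.9 and can act on them. This stands. But each of those routes is discretionary, and none sets a number that acts before subject 11.
- **Six is the extreme.** It needs five events in five subjects: 3% at a 50% rate and 17% at 70%, even with instant knowledge. When events spread over the treatment course, the mean is 1 to 2.
- **Extra subjects are informative for the review.** They add nothing to whether the fixed count is met, but they do refine the toxicity estimate that the PI and DISC would consider.
- **The words about acting at any time might signal that earlier action is intended.** They sit inside the opening condition, so the literal text does not allow it. If earlier action is the intention, the sentence needs the same edit.
- **The rule may never have been limited by the gate.** Appendix F shows that 12.6 was added in Version 5.1, dated September 2020, whereas Version 1.0 is dated January 2017. The documents do not report accrual at the time. If more than 10 subjects were already in, the gate had no effect. This cannot be settled from the documents.

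**Conclusion.** The point holds as a defect of wording with a modest effect on safety. The opening condition postpones a mandatory suspension after the fixed-count limb has been irreversibly met, and it buys that limb no reduction in false triggers.

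At true rates of 50% to 70%, the mean cost given a trigger runs from 1.2 to 2.1 further accruals (events uniform over about 3.7 months) up to 3.0 to 4.1 (events known at once), with a maximum of six. Where toxicity falls in that range of timings is an assumption, as are the true rates, independence between subjects and even accrual at 1.4 per month. The logical point, that the count cannot be undone and its trigger probability does not depend on the gate, needs none of the timing assumptions. Its practical effect depends on accrual having been 10 or fewer when the rule came into force.

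**What to change.** Reword 12.6 so that accrual is suspended for review as soon as 5 of the initial 10 treated subjects have a qualifying event, whatever the accrual at that time. Keep the condition of accrual above 10 only for the limb based on 50% or more of all treated subjects, where it guards against triggers on very small denominators.

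The cost is one sentence. The trigger probability of the fixed-count limb is unchanged. The downside is that the review may come earlier and so rest on fewer subjects' data. Before amending, confirm from the trial's records whether accrual had passed 10 when Version 5.1 took effect. If it had, the edit changes nothing in this trial.
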